### Adequacy of Protection Against Risks

#### A. Recruitment and Informed Consent

**Recruitment of Subjects**

Subjects who qualify for inclusion will be recruited for the study. Potential subjects will be identified by [name] who are experiencing pain with suboptimal pain relief by standard pain treatment. A randomization table for all subjects receiving pramipexole vs. placebo will be generated such that the Clinical Research Coordinator will use as a template when dispensing drug at the time of consent.

**B. Protections Against Risk**

**Confidentiality of Subjects**

Subjects will be assigned a study ID number. Linkage to name and other personal identifying information will be kept in a password-protected master database of enrolled subjects that will include subject name, date of birth, address, telephone numbers, race/ethnicity. The Brief Pain Inventory survey and records will be kept in a locked cabinet in a secure room by the CTSC Clinical Research Coordinator and will be accessible only to study staff. The computerized study database will only be accessible to study personnel using a password-protected system. For this study, we will utilize REDCap Survey, a secure, password protected data collection and management tool hosted by UNM's CTSC. Patients will use a study ID number to complete the electronic surveys to further ensure patient confidentiality. No personal identifying information will be used in data analysis or study reports. Subjects will sign also sign a HIPAA authorization as part of the informed consent process.

**Dose escalation risks**

Dose titration will increase by double if efficacy has not been achieved by the end of one week at the lower initial dose. A dose of 0.125 mg pramipexole once per night for 1 week is initiated for all subjects. At the end of week one, subjects will either increase the dose by double, 0.25 mg if pain relief is not satisfactory, or will remain at 0.125 mg if relief is satisfactory. A 2nd titration may occur at the end of week 2, with the dose escalating from 0.25 mg to 0.75 mg per night. Please see flow chart indicating the 'Dispensing Guideline', as an illustration.

Safety will be monitored either at the time the CRC asks the subject to provide their scores on the Brief Pain Inventory, or when the subject calls [name] reporting adverse experiences as indicated in safety endpoints. Upon consent, subjects will be instructed to call [name] should any adverse experiences noted in the 'safety endpoints' occur during the study period. After the study period is terminated, subjects will continue to see [name] in follow-up visits as needed.

All risks associated with pramipexole (Mirapex; Boehringer Ingelheim Pharmaceuticals) according to the manufacturer are:

1. Falling asleep during activities of daily living. Sudden onset of sleep may occur without warning. Somnolence is a common occurrence in patients receiving pramipexole at doses above 1.5 mg/day (0.5 mg three times a day). In controlled clinical trials in Restless Leg Syndrome, patients treated with MIRAPEX tablets at doses of 0.25-0.75 mg once a day, the incidence of somnolence was 6% compared to an incidence of 3% for placebo-treated patients.

2. Symptomatic orthostatic hypotension: Dopamine agonists, in clinical studies and clinical experience, appear to impair the systemic regulation of blood pressure, with resulting orthostatic hypotension, especially during dose escalation. Despite clear orthostatic effects in normal volunteers, the reported incidence of clinically significant orthostatic hypotension was not greater among those assigned to pramipexole tablets than among those assigned to placebo.

Symptomatic orthostatic hypotension will be monitored during dose escalation during weeks 1-2, as well as throughout the 4-week study. Monitoring will occur as detailed in “Collection and Reporting of Adverse Events”.

3. Impulse control/Compulsive behaviors: Patients may experience compulsive behaviors and other intense urges taking one or more of the medications, including pramipexole, that increase central dopaminergic tone and that are generally used for the treatment of Parkinson’s disease. For this reason, Parkinson’s Disease patients are not included in this study. However, if patients or their caregivers experience increased gambling urges, sexual urges, uncontrolled spending or other urges while being treated with pramipexole, subjects will be asked to report this to [name] and/or the CRC. [name] will consider dose reduction.
4. Hallucinations and Psychotic-like Behavior: The following symptoms are associated with patients with Parkinson’s Disease. In the three double-blind, placebo-controlled trials in early Parkinson's disease, hallucinations were observed in 9% (35 of 388) of patients receiving pramipexole tablets, compared with 2.6% (6 of 235) of patients receiving placebo.

Patients with a major psychotic disorder should ordinarily not be treated with dopamine agonists, including pramipexole, because of the risk of exacerbating the psychosis. In addition, certain medications used to treat psychosis may exacerbate the symptoms of Parkinson’s disease and may decrease the effectiveness of pramipexole. If a subject experiences hallucinations while taking pramipexole, pramipexole will be discontinued or reduced step-wise, pending the dose.

5. Dyskinesia: May be caused or exacerbated by pramipexole.
6. Renal impairment: Since pramipexole is eliminated through the kidneys, caution will be exercised in the current study.
7. Rhabdomyolysis, a condition in which the skeletal muscle rapidly breaks down leading to muscle pains, weakness, vomiting and confusion. A single case of rhabdomyolysis occurred in a 49-year-old male with advanced Parkinson's disease treated with Pramipexole tablets. The patient was hospitalized. The symptoms resolved with discontinuation of the medication.
8. Events reported with dopaminergic therapy: Include hyperpyrexia and confusion, fibrotic complications, and melanoma.

Most common adverse reactions (incidence >5% and greater than placebo):

1. Early PD without levodopa: nausea, dizziness, somnolence, insomnia, constipation, asthenia, and hallucinations.

2. Advanced PD with levodopa: postural (orthostatic) hypotension, dyskinesia, extrapyramidal syndrome, insomnia, dizziness, hallucinations, accidental injury, dream abnormalities, confusion, constipation, asthenia, somnolence, dystonia, gait abnormality, hypertonia, dry mouth, amnesia, and urinary frequency.
3. RLS: nausea, somnolence, fatigue, and headache

In the event of an adverse event, the HRRC will be notified. An adverse event case report from will be completed. The CRC will notify [name] and [name] as well as the appropriate personnel in the HRRC. It is important to note that a standardized form will be used for adverse event reporting. The form will ask the following questions:

1. Have you experienced any unusual events since you were last seen here? If yes, the CRC will probe further and ask:
2. What exactly did you experience?
3. Did you seek treatment for this experience?
4. Were you given any medications. What was the dose and date started? Are you still taking this medication? If no, when did you stop taking this medications? and should specifically
5. Have you been feeling dizzy and have you experienced any falls?

In addition, the opinion of [name] will note on the adverse event case report from if this adverse event was associated with the study drug, pramipexole.

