## **7. Study Endpoints**

- 7.4. The primary endpoint is the paper-and-pencil survey, the Brief Pain Inventory. The secondary study endpoints will be mRNA and protein analysis from blood samples provided at the initiation and terminal of the study.
- 7.5. *Safety endpoints of the study will include the following: (1) Worsening of pain score or increased verbal dissatisfaction with pain relief, (2) sudden onset of sleep without warning, (3) intense urges, (4) hallucinations and/or psychotic-like behaviors, (5) fever, and (6) orthostatic hypotension. While the patients who experience these adverse events, dosing with pramipexole will require a 50% step-wise reduction over a period of two weeks. Given the maximal allowable dose is 0.75 mg, this prescribed step-wise reduction is well within the manufacturer's recommended tapering of pramipexole, which the recommended dose reduction is 0.375 per day.*
- 7.6. No exploratory endpoint are in the current study.

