### **Week 4**

1 Red at 0.125 mg/day OR 2 Red at 0.125 mg/day to achieve 0.250/day, OR 1 green at 0.250 mg/day OR 2 green to achieve 0.5 mg/day, OR 3 green to achieve 0.750 mg/day.

	Week 1	Week 2	Pills needed/ Dispense @ enrollment visit	Week 3	Week 4	Pills needed/ Dispense at midterm
Scenario 1	1 Red	1 Red	14 Red	1 Red	1 Red	14 Red

Scenario 2	1 Red	1 Red	14 Red	1 Red	2 Red	21 Red
Scenario 3	1 Red	2 Red	21 Red	1 Green	1 Green	14 Green
Scenario 4	1 Red	2 Red	21 Red	1 Green	2 Green	21 Green
Scenario 5	1 Red	2 Red	21 Red	2 Green	2 Green	28 Green
Scenario 6	1 Red	2 Red	21 Red	2 Green	3 Green	35 Green

Yellow highlight indicates number of pills at Dispense time.

1st Dispense (week 1)

21 Red pills

2nd Dispense (week 3)

Either 21 Red pills (week 3 subject still at 1 Red)

OR 35 Green pills (any other scenario)

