## **15. Withdrawal of Subjects**

Anticipated circumstances where subjects may be withdrawn from the research without their consent may be if their pain scores worsen for longer than a week.

In the event of early withdrawal, patients will be tapered from 0.5 (if currently taking that dosage) to 0.250 for 1 week. However, according to the manufacturer's (Boehringer Ingelheim, Inc) packet information, pramipexole at doses of up to 0.75 once daily can be discontinued without taper.

While there are no contraindications associated with pramipexole, the collection and reporting of adverse are as follows:

The collection and reporting of adverse events will occur at: (1) the time of the phone conversation at the end of weeks 1 and 3 with the CRC who will collect the Brief Pain Inventory scores, (2) at the end of week 2, the time of the mid-term in-person meeting with the CRC when the subject will provide the scores of the BPI for that week and will pick up drug dispense #2, (3) At the final in-person with the CRC, at the termination of the study at week 4, and (4) at any point during the study when the subject calls the CRC to report an adverse event or when the subject calls [name]. All adverse events will be recorded by the CRC and kept with the subject's study records.

See actions upon evidence of symptomatic orthostatic hypotension above (Section 14, "Provisions to monitor the data to ensure the safety of subjects"), and other adverse

reactions will be monitored during dose escalation during weeks 1-2, as well as throughout the 4-week study. Monitored will occur as detailed in “Collection and Reporting of Adverse Events”.

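### Orthostatic hypotension is a declared safety endpoint, but no blood pressure reading is scheduled; the escalation weeks and the cross-reference to actions also need correcting

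*Combined protocol and SAP*

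**What the plan says.** Section 7.5 (Study Endpoints) lists six safety endpoints, the last two given as "5) fever, and (6) orthostatic hypotension". For subjects who experience any of them it states that "dosing with pramipexole will require a 50% step-wise reduction over a period of two weeks".

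Section 14, under Dose escalation risks, states: "Symptomatic orthostatic hypotension will be monitored during dose escalation during weeks 1-2, as well as throughout the 4-week study". The Safety Monitoring Plan in the same section and Section 15 (Withdrawal of Subjects) use the same timing. Adverse events are collected by phone at the end of weeks 1 and 3, in person at the end of weeks 2 and 4, and whenever a subject calls. The adverse-event form has open questions and one specific prompt: "Have you been feeling dizzy and have you experienced any falls".

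On dose, Section 14 says "A dose of 0.125 mg pramipexole once per night for 1 week is initiated for all subjects", after which "subjects will either increase the dose by double, 0.25 mg if pain relief is not satisfactory". The Week 4 dispensing list in Section 12 runs up to "OR 2 green to achieve 0.5 mg/day, OR 3 green to achieve 0.750 mg/day". Section 13 instead caps the daily dose at 0.5 mg.

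On what happens if the event occurs, Section 15 says "See actions upon evidence of symptomatic orthostatic hypotension above (Section 14".

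**The concern.** An endpoint named as orthostatic hypotension implies a fall in blood pressure on standing. If no pressure is measured, what is collected is a symptom, and the two can differ in both directions: dizziness from another cause can be counted as hypotension, and a pressure fall without symptoms is never seen. All subjects stay on their standard pain treatment, and the protocol itself warns about sedating co-medication, so unsteadiness from other causes is foreseeable in both arms.

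At stake are the safety table by arm, the events that feed the interim safety review after the 15th participant, and the consistency with which staff apply the dose-reduction statement in Section 7.5. The escalation label and the cross-reference matter less, but both tell staff where to look, and both direct them wrongly.

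**Working it through.** **1. Endpoint against procedures.** These are the places where a reading could be scheduled, and what each contains:

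- Section 4.1, data collected at screening: demographics, weight, height, menopausal and surgical history, years of pain treatment, diagnosis and insurance. No blood pressure.
- Sections 9, 12 and 22, visit content: consent, Brief Pain Inventory, blood draw, dispensing and return of drug, questions. No blood pressure or other vital sign.
- Section 14: blood pressure is mentioned only in the background account of the drug class.

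Readings described: 0 of 3 in-person visits (start, end of week 2, end of week 4), and no baseline. The one specific prompt asks about dizziness and falls together and does not mention standing up. Its layout leaves unclear whether it is put to everyone or only after a positive answer to the first question. In its list of reactions in advanced Parkinson's disease, Section 14 gives postural hypotension and dizziness as separate entries.

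Size of one misclassified subject, assuming equal allocation (the protocol does not state the ratio): with 30 subjects, 1/15 = 6.7 percentage points of an arm's rate; with the maximum of 45 recruited, 1/22.5 = 4.4 points.

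**2. Escalation weeks.** Inputs are the six scenarios in the dispensing tables of Sections 12 and 31, with red = 0.125 mg and green = 0.25 mg. As a check on the reading, the capsule counts reproduce: for example, Scenario 5's second dispense is 7×2 + 7×2 = 28 and Scenario 6's is 7×2 + 7×3 = 35.

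Share of the rise after week 2 = (week 4 dose − week 2 dose) / (week 4 dose − week 1 dose).

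| Scenario | Dose in weeks 1, 2, 3, 4 (mg/day) | Total rise | After week 2 | Share |
|---|---|---|---|---|
| 1 | 0.125, 0.125, 0.125, 0.125 | 0 | 0 | none |
| 2 | 0.125, 0.125, 0.125, 0.25 | 0.125 | 0.125 | 100% |
| 3 | 0.125, 0.25, 0.25, 0.25 | 0.125 | 0 | 0% |
| 4 | 0.125, 0.25, 0.25, 0.5 | 0.375 | 0.25 | 66.7% |
| 5 | 0.125, 0.25, 0.5, 0.5 | 0.375 | 0.25 | 66.7% |
| 6 | 0.125, 0.25, 0.5, 0.75 | 0.625 | 0.5 | 80% |

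The narrative path in Section 14 (0.25 to 0.75 mg at the end of week 2) also gives (0.75 − 0.25)/(0.75 − 0.125) = 80%. Under the 0.5 mg cap in Section 13, the largest path gives (0.5 − 0.25)/(0.5 − 0.125) = 66.7%. Four of the five escalating scenarios have an increase after week 2, so the weeks 1-2 label does not match the schedule under either top dose.

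**3. Cross-reference.** Section 14 contains monitoring, reporting and enrolment-suspension rules. It states a response for compulsive urges and for hallucinations, but none for orthostatic hypotension. The only action that covers this endpoint is the general one in Section 7.5. Section 15 separately describes a one-week taper on early withdrawal, starting from 0.5 mg, while Section 7.5 refers to a two-week reduction and a 0.75 mg maximum.

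**The case against.** The strongest defence is that the protocol monitors the symptomatic form, says so in Section 14, and does so for the whole study. Each week has a scheduled contact. Subjects are told at consent to call the physician if any listed safety endpoint occurs. The form asks open questions and records the physician's opinion on association with the drug. Section 9.5 lets the physician order diagnostics, so a reported event can be verified. Section 14 also reports that clinically significant orthostatic hypotension was no more frequent on pramipexole than on placebo, and its list of common reactions in Restless Legs Syndrome, the indication whose dosing this trial follows, does not include dizziness.

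Much of this stands. It rules out several stronger readings that a reader might infer:

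- That monitoring stops after week 2. The quoted sentence extends it to all four weeks, with the same weekly ascertainment; only the escalation label is wrong.
- That 80% of the dose increase generally comes late. That is Scenario 6; the range over escalating scenarios is 0% to 100%. In relative terms Scenario 6 doubles at week 2, doubles at week 3 and rises 1.5-fold at week 4, so the later steps are larger only in milligrams.
- That no action exists. One does, in Section 7.5; the reference is misdirected.
- That ascertainment rests on a single question, or is absent. It is by symptom report through several routes.

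The defence does not supply a measurement. Unscheduled verification depends on who complains and has no baseline to compare with, and Section 7.5 does not limit the endpoint to symptoms.

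**Conclusion.** The point holds in this form: the endpoint is named for a measurement that the described procedures do not take. Symptom reports can be tabulated, but they are not an orthostatic hypotension rate, and the arms cannot validly be compared on one. This is worth correcting before enrolment. The escalation label and the cross-reference are minor taken alone.

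The documents do not support a claim that subjects go unmonitored during later increases, or that an excess of hypotension is expected at these doses.

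The conclusion rests on the procedures as described. The weekly screening script and the eligibility table are referred to but are not in the text available; if either schedules a reading, the first part falls away. The figures for one misclassified subject assume equal allocation.

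**What to change.** - Record seated (or lying) and standing blood pressure at the three existing visits. Report the readings by arm alongside the symptom reports. State the limits: the first reading is before drug, the week 2 reading follows at most 0.25 mg, only the week 4 reading follows the later increases, and daytime readings after a bedtime dose may miss the peak effect. The dizziness question therefore stays, and the form should say whether everyone is asked it.
- If readings are not taken, rename the sixth safety endpoint as self-reported dizziness or falls, so that no hypotension rate is claimed.
- In Sections 14 and 15, correct the escalation weeks to those in which the dispensing tables allow increases.
- Have the sponsor reconcile Sections 7.5, 13 and 15 on the action for this event and on the top dose (0.5 or 0.75 mg), and point Section 15 to the text that states the action. This review proposes no dose or reduction rule, and the readings are for reporting, not a new trigger for dose reduction.

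Cost: a few minutes with a cuff per visit, or 3 × 30 = 90 to 3 × 45 = 135 paired readings in all, at visits already held. The rest is wording.

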### Safety Monitoring Plan:

While there are no contraindications associated with pramipexole, the collection and reporting of adverse are as follows:

The collection and reporting of adverse events will occur at: (1) the time of the phone conversation at the end of weeks 1 and 3 with the CRC who will collect the Brief Pain Inventory scores, (2) at the end of week 2, the time of the mid-term in-person meeting with the CRC when the subject will provide the scores of the BPI for that week and will pick up drug dispense #2, (3) At the final in-person with the CRC, at the termination of the study at week 4, and (4) at any point during the study when the subject calls the CRC to report an adverse event or when the subject calls [name]. All adverse events will be recorded by the CRC and kept with the subject's study records.

Symptomatic orthostatic hypotension and other adverse reactions will be monitored during dose escalation during weeks 1-2, as well as throughout the 4-week study, as part of the routine contact with participants.

The HRRC will be notified as per usual rules within five business days after the PI becomes aware of any severe adverse events, as defined by the Common Terminology Criteria for Adverse Events (CTCAE) version 5.0, published 11/27/2017 by the National Cancer Institute. The CTCAE defines adverse events of grade 3 or higher as “severe.”

Safety monitoring will occur in two tracks. In one track, monitoring will occur as part of the routine (weekly) study-related contact. Study personnel will include screening for adverse events as noted in the included script. The PI will be notified promptly of any moderate or severe adverse events identified in this screening process. All screening information will be provided to the PI for review in the second track of the monitoring procedure, and for entry in a Non-Reportable Log, as appropriate.

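### The adverse-event form has no direct item for four of the six safety endpoints; unless the weekly screening script asks about them, they rest on an open question and self-report and may be under-counted

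*Combined protocol and SAP*

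**What the plan says.** **Endpoints.** Section 7.5 lists six safety endpoints. The first concerns pain ("1) Worsening of pain score or increased verbal dissatisfaction with pain relief"). The other five are "2) sudden onset of sleep without warning, (3) intense urges, (4) hallucinations and/or psychotic-like behaviors, (5) fever, and (6) orthostatic hypotension".

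**The form.** Near the end of the Dose escalation risks text in Section 14, the protocol says that a standardized form will be used for adverse-event reporting and lists its questions. The opening item is "Have you experienced any unusual events since you were last seen here? If yes, the CRC will probe further and ask". Items 2 to 4 ask what happened, whether treatment was sought and what medication was given. Item 5 is the only one that names a symptom: "Have you been feeling dizzy and have you experienced any falls". A broken sentence fragment stands just before item 5, so the text does not settle whether that item is put to everyone or only after a yes to item 1.

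**Other routes of capture.**
- Safety Monitoring Plan, weekly contacts: "Study personnel will include screening for adverse events as noted in the included script". The script itself is not among the documents reviewed.
- Dose escalation risks: at consent, subjects are instructed to call the study physician "should any adverse experiences noted in the 'safety endpoints' occur during the study period".
- Dose escalation risks, on impulse control: if patients or caregivers "experience increased gambling urges, sexual urges, uncontrolled spending or other urges while being treated with pramipexole, subjects will be asked to report this".
- Safety Monitoring Plan, repeated in Section 15: reports are also accepted "at any point during the study when the subject calls the CRC to report an adverse event".

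**What uses the counts.** The interim review takes place within one week of the 15th enrollment. It covers events found in screening and direct reports to an investigator. The HRRC is notified if three or more active-arm patients have had events of CTCAE grade 2 or higher. Separately, a second event of grade 3 or higher among participants suspends enrollment.

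**The concern.** The form and the endpoint list do not match. Dizziness and falls are prompted by name; sudden sleep, urges, hallucinations and fever are not. A patient asked only about unusual events may not think of gambling or spending urges in those terms, or may be reluctant to raise them. A blank on the form for these four endpoints would then mean either that nothing happened or that nothing was mentioned.

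Two things are at stake. The interim review, the three-patient trigger and the suspension rule all work on recorded events, so incomplete recording makes each of them slower to act. In addition, with one type of event prompted and four not, the adverse-event profile that the trial reports may partly reflect how the form is built.

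**Working it through.** **Step 1. Map each endpoint in Section 7.5 to a direct question.**

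| Safety endpoint | Direct item on the form | Other scheduled instrument |
|---|---|---|
| 1. Pain worsening or verbal dissatisfaction | none | weekly Brief Pain Inventory (the score part; verbal dissatisfaction only indirectly) |
| 2. Sudden onset of sleep | none | script, text not available |
| 3. Intense urges | none | script, text not available |
| 4. Hallucinations, psychotic-like behavior | none | script, text not available |
| 5. Fever | none | script, text not available |
| 6. Orthostatic hypotension | dizziness and falls (a symptom proxy) | script, text not available |

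Endpoints without a direct form item and not covered by the pain inventory: numbers 2, 3, 4 and 5, which is 4 of 6. If the dizziness item is asked only after a yes to item 1, orthostatic hypotension has the same weakness and the count becomes 5 of 6. No blood-pressure measurement is described for that endpoint.

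**Step 2. Sort the other routes.** The consent instruction, the request to report urges and the unscheduled calls are endpoint-aware, but the patient has to start them. None puts the same question to every patient at each contact. The script is the one route that could do so, and its content is unknown here.

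**Step 3. Is there a figure to reproduce?** No. The documents give no capture rate and no expected rate of grade 2 or higher events in this population. The size of any under-count cannot be derived.

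**Step 4. Illustration only: how sensitive is the three-patient trigger to incomplete capture?**

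Assumptions, none of them from the protocol:
- Allocation is equal, so the 15 enrolled at the interim review give 7 or 8 active patients.
- The true per-patient probability *p* of a grade 2 or higher event is 0.20 or 0.30.
- A fraction *s* of affected patients is recorded.

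With q = p × s, P(trigger) = 1 − Σ C(n,k) qᵏ (1 − q)ⁿ⁻ᵏ, summed over k = 0, 1, 2.

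For n = 8 and p = 0.30:
- s = 1 (q = 0.30): 1 − (0.058 + 0.198 + 0.296) = 0.448
- s = 0.5 (q = 0.15): 1 − (0.272 + 0.385 + 0.238) = 0.105

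| Active patients n | p | s = 1 | s = 0.75 | s = 0.5 |
|---|---|---|---|---|
| 8 | 0.30 | 0.448 | 0.260 | 0.105 |
| 8 | 0.20 | 0.203 | 0.105 | 0.038 |
| 7 | 0.30 | 0.353 | 0.194 | 0.074 |
| 7 | 0.20 | 0.148 | 0.074 | 0.026 |

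With so few patients, a moderate loss of events lowers the chance of reaching the trigger by a large factor. The table applies *s* to all grade 2 or higher events. If only the four unprompted endpoints are affected, the drop is smaller. It shows direction and sensitivity, and does not forecast this trial.

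**The case against.** The strongest reply is that the form is not the only instrument, and perhaps not the screening instrument at all. Section 14 introduces it in the context of an adverse event having occurred, so it may be a case-report form completed once an event is known. Screening proper is assigned to the weekly script, which may well ask about all six endpoints. Patients are also told at consent what to call about, urges get their own reporting request, and direct reports to an investigator feed the interim review.

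Much of this stands. A reader might infer that the four endpoints depend entirely on one open question, that nobody asks about them by name, or that they will be under-counted. The documents support none of these. The first overlooks the other routes. The second cannot be asserted without the script. The third is a prediction with no capture rate behind it.

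A reader might also try to size the problem from the hallucination rate that the protocol quotes, 35 of 388 (9%). With 15 active patients that gives 15 × 35/388 = 1.35 expected cases and a 1 − (1 − 0.0902)¹⁵ = 76% chance of at least one, falling to 34% or 50% if only 30% or 50% of cases are captured. The arithmetic is right, but it should not carry weight:
- The rate comes from early Parkinson's disease, which this trial excludes.
- The placebo rate beside it is 6 of 235 (2.6%).
- The capture fractions are assumed.
- The interim trigger is assessed with about 7 or 8 active patients, and it counts grade 2 or higher events.

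The reply does not remove two points. Item 1 of the form is worded as a screening question, so the form and the script at least overlap. And the routes that can be read in the documents are all patient-initiated.

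**Conclusion.** The point holds in a conditional form. It is established from the text that four of the six safety endpoints have no direct item on the standardized form, and that the dizziness and falls item may itself be conditional. If the weekly script does not name those endpoints, their capture rests on an open question and self-report, and they may be under-counted wherever the protocol acts on event counts. If the script does name them, what remains is a mismatch between form, script and Section 7.5 that should be reconciled.

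The size is unknown. The trigger probabilities above depend on assumed event rates, assumed capture and equal allocation; they show only that a three-patient rule with 7 or 8 active patients is sensitive to missed events. This is a cheap improvement to safety ascertainment and does not show that the monitoring plan fails.

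**What to change.** Align the form and the weekly script with Section 7.5:

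1. Add four fixed yes/no items, asked of every patient whatever the answer to item 1: sudden sleep; new or stronger urges (gambling, sexual, spending or other); hallucinations or unusual beliefs; fever.
2. Repair the broken text before item 5 and state that the dizziness and falls item is asked of everyone.
3. Use identical wording in both arms at each existing contact (weeks 1 to 4, by phone or in person).
4. State whether the form or the script is the screening instrument. If the script already contains these items, carry its wording into the form.

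This needs no new visits and changes no dosing or clinical rule. The cost is about one minute per contact, which is an estimate. The real downside is that direct questions will bring in more minor events in both arms, which may bring the grade 2 trigger nearer. The interim review should therefore record which events were prompted and which were volunteered.
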